3. STUDY DESIGN

3.1. Overall Design

This is a Phase 2, multicenter, randomized, double-blind, placebo-controlled study to assess the safety and efficacy of etrasimod 2 mg and 3 mg, once daily for up to 52 weeks in subjects with moderate-to-severe AA. The study includes multiple periods: A \leq 4-week Screening Period (to determine subject eligibility), a 24-week Double-Blind Treatment Period, a 28-week Open-Label Extension Period, and a 4-week Safety Follow-Up Period for a maximum total study duration of 60 weeks.

This study will include approximately 78 subjects with moderate-to-severe AA with current episode of hair loss for \geq 6 months but $<$ 5 years (current episode must also be relatively stable during the last 6 months with no significant regrowth).

Subjects will be separated into 2 cohorts as follows:

Cohort 1: All subjects (approximately 36 subjects) enrolled under the original protocol, and Amendments 0.1, 0.2, 1.0, and 1.1.

[figure not shown]
Subjects were randomized in a 2:1 ratio to receive etrasimod 2 mg or placebo orally, once daily. Randomization was stratified by SALT I score ($<$ 100, 100) at Day 1/Baseline. Subjects will complete the Double-Blind Treatment Period per their original randomization assignment. Subjects who have entered the Open-Label Extension Period prior to Amendments 2.0 and 2.1 implementation will transition to 3 mg once daily at their next study visit. Subjects who have not entered the Open-Label Extension Period prior to Amendments 2.0 and 2.1 implementation will receive etrasimod 2 mg from the Week 24 visit to the Week 25 visit and will transition at the Week 25 visit to etrasimod 3 mg orally, once daily for the remainder of the Open-Label Extension Period. Of note, subjects already in the Open-Label Extension Period at the time of

Amendments 2.0 and 2.1 implementation may be allowed to continue on etrasimod 2 mg at the Investigator’s discretion provided that they have achieved a SALT I score ≤ 20 .

Cohort 2: All subjects (approximately 42 subjects) enrolled under protocol Amendments 2.0 and 2.1.

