3.2. Discussion and Scientific Rationale for Study Design

This Phase 2 study will be a randomized, double-blind, placebo-controlled, safety and efficacy study that is intended to support the development of etrasimod 2 mg and 3 mg for the treatment of moderate-to-severe AA. The subjects will be those with moderate-to-severe AA with current episode of hair loss for at least 6 months but less than 5 years (current episode must also be relatively stable during the last 6 months with no significant regrowth).

This study will assess etrasimod 2 mg and 3 mg monotherapy compared to placebo during the first 24 weeks of treatment. The choice of placebo as a control is appropriate for the objectives of this study since it will provide the most robust assessment of the safety and efficacy of etrasimod. The 24-week treatment duration was selected to ensure that etrasimod could reach its maximal efficacy with respect to hair regeneration while minimizing the time that a subject may be on placebo treatment. As this is a placebo-controlled study, the duration is limited. Subjects from Cohort 1 who are already in the Open-Label Extension Period at the time of Amendments 2.0 and 2.1 implementation may be allowed to continue on etrasimod 2 mg at the Investigator's discretion provided that they have achieved a SALT I score ≤ 20 . All other subjects who continue to the Open-Label Extension Period, will receive etrasimod 3 mg once daily for a total etrasimod treatment duration of up to 52 weeks. The Open-Label Extension is designed to allow subjects to continue etrasimod therapy and to assess long-term safety and efficacy of 3 mg once daily dosing as a chronic therapy.

Efficacy will be assessed by percent change in hair loss using a well-validated metric and widely utilized tool (SALT I score) at each visit, with a primary endpoint of percent change in SALT I score from Baseline to end of the Double-Blind Treatment Period (Week 24).

Additionally, because patient-reported outcomes (PROs) can provide subject perspectives on aspects of their disease conditions and overall health status, several PROs will be explored in this study. The Alopecia Areata Symptom Impact Scale (AASIS) and Alopecia Areata Quality of Life Index (AA-QLI) will be administered every 12 to 16 weeks at study visits.

Exploratory measures will include cytokine and chemokine analysis of serum samples.

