11.2. Determination of Sample Size

Subjects will be randomized as follows:

- Cohort 1: 36 subjects in 2:1 randomization ratio (24 subjects to etrasimod 2 mg and 12 subjects to placebo)
- Cohort 2: 42 subjects with SALT I < 95 at Baseline in 4:1:2 randomization ratio (24 subjects to etrasimod 3 mg, 6 subjects to etrasimod 2 mg, and 12 subjects to placebo)

Assuming a 15% drop-out rate from the study over 24 weeks, at least 35 treatment completers (20 subjects to etrasimod 3 mg, 5 subjects to etrasimod 2 mg, and 10 subjects to placebo from Cohort 2; plus subjects from Cohort 1 with SALT I < 95 at Baseline) at Week 24 will provide at least 80% and 47% power to detect a treatment difference of 20% for etrasimod 3 mg and etrasimod 2 mg from placebo, respectively, in the percent change from Baseline in SALT I at Week 24 by a 2-sample t-test using a 2-sided significance test level of 0.05 and common standard deviation (SD) of 17.8%.

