3 STUDY DESIGN

3.1 Design Overview

This is a Phase 2, multicenter, randomized, double-blind, placebo-controlled study to assess the safety and efficacy of etrasimod 2 mg and 3 mg, once daily for up to 52 weeks in subjects with moderate-to-severe AA. The study includes multiple periods: a \leq 4-week Screening Period (to determine subject eligibility), a 24-week DB Treatment Period, a 28-week OLE Period, and a 4-week Safety Follow-Up (SFU) Period for a maximum total study duration of 60 weeks.

This study will include approximately 78 subjects (36 in Cohort 1 and 42 in Cohort 2 as described below) with moderate-to-severe AA with current episode of hair loss for \geq 6 months but $<$ 8 years in Cohort 1 and hair loss for \geq 6 months and $<$ 5 years in Cohort 2 (current episode must also be relatively stable during the last 6 months with no significant regrowth).

[figure not shown]
Subjects will be separated into 2 cohorts as follows:

Cohort 1: All subjects (approximately 36 subjects) enrolled under the original protocol, and Amendments 0.1, 0.2, 1.0, and 1.1.

Subjects will be randomized in a 2:1 ratio to receive etrasimod 2 mg or placebo orally, once daily. Randomization is stratified by SALT I score (< 100 , 100) at Day 1/Baseline. Subjects will complete the DB Treatment Period per their original randomization assignment. Subjects who have entered the OLE Period prior to Amendments 2.0 and 2.1 implementation will transition to 3 mg once daily at their next study visit. Subjects who have not entered the OLE Period prior to Amendments 2.0 and 2.1 implementation will receive etrasimod 2 mg from the Week 24 visit to the Week 25 visit and will transition at the Week 25 visit to etrasimod 3 mg orally, once daily for the remainder of the OLE Period. Of note, subjects already in the OLE Period at the time of Amendments 2.0 and 2.1 implementation may be allowed to continue on etrasimod 2 mg at the Investigator's discretion provided that they have achieved a SALT I score ≤ 20 .

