Cohort 2: All subjects (approximately 42 subjects) enrolled under protocol Amendments 2.0 and 2.1. Subjects will be randomized in a 4:1:2 ratio to receive etrasimod 3 mg, etrasimod 2 mg, or placebo orally, once daily, in a double-blind manner for the 24-week DB Treatment Period. Randomization will be stratified by SALT I score (< 50 , ≥ 50) at Day 1/Baseline. During the DB Treatment Period, subjects assigned to etrasimod 3 mg will receive etrasimod 2 mg orally, once daily from Day 1 to the Week 1 visit and will transition at the Week 1 visit to etrasimod 3 mg orally, once daily for the remainder of the DB Treatment Period. During the OLE Period, all subjects will receive etrasimod 2 mg orally, once daily from the Week 24 visit to the Week 25 visit. At the Week 25 visit all subjects will transition to 3 mg orally, once daily for the remainder of the OLE Period.

Figure 1: Schematic Diagram of Study Design

^a Randomized 2:1 (etrasimod 2 mg:placebo) in the Double-Blind Treatment Period.

^b Subjects entering the Open-Label Extension Period (Week 24 visit) before implementation of Amendments 2.0 and 2.1 will transition to 3 mg once daily at their next study visit (refer to Section 10.5.7.5 and Appendix 1 of the protocol for additional information on Holter monitoring). Subjects entering the Open-Label Extension Period (Week 24 visit) after implementation of Amendments 2.0 and 2.1 will receive etrasimod 2 mg from the Week 24 visit to the Week 25 visit and will transition to etrasimod 3 mg at the Week 25 visit. Of note, subjects already in the Open-Label Extension Period at the time of Amendments 2.0 and 2.1 implementation may be allowed to continue on etrasimod 2 mg at the Investigator’s discretion provided that they have achieved a SALT I score ≤ 20 .

^c SFU 1 and SFU 2 are to be conducted 2 and 4 weeks (± 3 days) after last dose of study drug, respectively.

^d Randomized 4:1:2 (etrasimod 3 mg:etrasimod 2 mg:placebo) in the Double-Blind Treatment Period.

* Subjects will initiate treatment on 2 mg etrasimod for 1 week prior to starting 3 mg.

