5 STATISTICAL CONSIDERATIONS

5.1 Analysis Sets

The following analysis sets will be defined for the DB Treatment Period and OLE Period separately:

Table 2. Summary of Analysis Sets

Analysis Set	Description
DB Treatment Period	
Randomized Set	
The Randomized Set includes all randomized subjects, irrespective of whether they received any study drug.
 
All subjects will be analyzed according to the treatment group to which they were randomized.

Full Analysis Set (FAS)	
The FAS includes all randomized subjects with a SALT I < 95 at Baseline who received at least one dose of study drug. The FAS will be used for the primary analysis of the primary efficacy endpoint and main analysis of the secondary, exploratory, and other efficacy endpoints.
 
All subjects will be analyzed according to the treatment group to which they were randomized.

Modified Full Analysis Set (mFAS)	
The mFAS consists of all randomized subjects with a SALT I < 95 at Baseline who received at least 1 dose of study drug, have a Baseline measurement, and have at least 1 post-randomization measurement.
 
The mFAS is endpoint specific, therefore subjects included in the analysis set for 1 endpoint may differ from another endpoint, based on the Baseline and post-Baseline data. The mFAS will be used for sensitivity analyses for the primary and secondary endpoints in SALT I.
 
All subjects will be analyzed according to the treatment group to which they were randomized.

Analysis Set	Description
Per Protocol Set (PPS)	
The PPS consists of all subjects in the FAS with no major protocol deviations (PD) potentially having an impact on the SALT I-related primary and secondary efficacy endpoints (refer to Sections 7.2 and 10.1).
 
The PPS will be used for sensitivity analyses for the primary and secondary efficacy endpoints in SALT I to evaluate the influence of major PD potentially having an impact on the efficacy endpoints.
 
All subjects will be analyzed according to the treatment group to which they were randomized.

Safety Set (SAF)	
The SAF consists of all randomized subjects who received at least 1 dose of study drug.
 
All safety analysis in the DB Treatment Period will be performed using SAF. All subjects will be analyzed according to the actual treatment they received. In case a subject received more than one actual treatment, the first treatment received will be used for the safety analysis.

OLE Period	

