5.2 Adjustments for Covariates

For the continuous efficacy endpoints (e.g., change and percent change from baseline), disease duration and baseline value will be included as covariates in the statistical models, where disease duration, in years, will be calculated as follows:

$$\text{Disease duration (years)} = (\text{Randomization date} - \text{Initial onset date} + 1) / 365.25$$

Should the day be missing for the initial onset date, it will be imputed to the 1st of the month. Should both the day and month be missing for the initial onset date, they will be imputed to January 1st. Completely missing initial onset date will not be imputed.

For binary efficacy endpoints, Cochran-Mantel-Haenszel (CMH) tests will be stratified by the stratification factor for SALT I based on the value used by the IWRS at the time of randomization. If there are more than 10% of subjects who were mis-stratified, a sensitivity analysis will be conducted using the value from the clinical database.

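### Cohort 1 admitted current episodes under 8 years, so episodes of 5 years or more can occur only on placebo and 2 mg, and the primary MMRM has neither a cohort nor a current-episode term

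*Protocol*

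**What the plan says.** **Population.** Protocol 3.1 opens with "This study will include approximately 78 subjects with moderate-to-severe AA with current episode of hair loss for" 6 months to under 5 years and draws no distinction between cohorts. Protocol 3.2 repeats the limit: "current episode of hair loss for at least 6 months but less than 5 years". SAP 3.1 splits it, putting the upper limit at "8 years in Cohort 1 and hair loss for" 6 months to under 5 years in Cohort 2. SAP Table 4, which lists departures from the protocol, does not mention this. The protocol does keep cohort-specific limits for SALT I (section 10.3.1), so the missing split for episode duration looks like an omission.

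**Allocation.** For Cohort 1: "Subjects will be randomized in a 2:1 ratio to receive etrasimod 2 mg or placebo orally, once daily". For Cohort 2: a "4:1:2 ratio to receive etrasimod 3 mg, etrasimod 2 mg, or placebo orally, once daily".

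**Analysis set.** SAP 5.1: "The FAS includes all randomized subjects with a SALT I < 95 at Baseline who received at least one dose of study drug". The set carries no condition on episode duration.

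**Model.** SAP 5.2 says that "disease duration and baseline value will be included as covariates in the statistical models", and computes disease duration from the initial onset date. SAP 6.1 lists duration of the current episode as a separate variable. The primary MMRM in SAP 10.1 contains treatment, visit, their interaction, disease duration as defined in 5.2, and baseline SALT I.

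**Where current-episode duration appears.** SAP 5.7 plans FAS subgroups by current episode, including a class of 5 years or more, with descriptive statistics only.

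**The concern.** Two entry limits changed between the cohorts: SALT I and length of the current episode. The FAS brings Cohort 1 into line with the new SALT I limit but not with the new duration limit. SAP 5.7 shows that the sponsor expects episodes of 5 years or more in the FAS, and no eligible Cohort 2 subject can be in that class. Such subjects can therefore be on placebo or 2 mg but not on 3 mg.

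The existing covariate does not measure what differs. Protocol 1.1 says that most patients have their first patch before adulthood and that relapse can come at any time, while subjects are aged 18 to 70. Someone can have decades since onset and a short current episode. For a first episode the two durations coincide, so the covariate is a partial proxy.

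At stake is the headline estimate. If longer episodes regrow less, the pooled placebo arm is held down relative to 3 mg, and the 2 mg arm is held down relative to placebo. The premise is not established in the documents. Protocol 1.1 says only that success with available treatments depends on how extensive and how long-standing the disease is.

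**Working it through.** **1. The plan's own power figures** (Protocol 11.2, SAP 3.2). Two-sample t-test, difference 20, SD 17.8, two-sided 0.05, power from the noncentral t distribution.
- 3 mg, 20 v 10 completers: 20 / (17.8 × √(1/20 + 1/10)) = 2.90 on 28 df, power 79.97% (stated: 80%).
- 2 mg, 5 v 10 completers: 20 / (17.8 × √(1/5 + 1/10)) = 2.05 on 13 df, power 47.6% (stated: 47%).
- Dropout: 24, 6 and 12 × 0.85 = 20.4, 5.1 and 10.2, which agrees with 20, 5 and 10.

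Both figures are reproduced. They rest on Cohort 2 completers alone, so this point does not affect them.

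**2. Planned share of each pooled arm from Cohort 1.** Placebo 12/24 = 50%; 2 mg 24/30 = 80%; 3 mg 0/24 = 0%. If a fraction r of Cohort 1 survives the SALT I trim, the shares are 12r/(12r + 12) and 24r/(24r + 6). At r = 0.5 they are 33% and 67%.

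**3. Assumptions (none is in the documents).**
- r = 0.5 to 1.
- q, the share of retained Cohort 1 subjects with an episode of 5 years or more, = 20% to 40%. The upper value follows from a uniform spread: (8 − 5)/(8 − 0.5) = 40%.
- d, the shortfall in Week 24 improvement for such episodes, = 5 to 15 points.
- The existing covariates absorb none of it.

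**4. Bias.** For 3 mg versus placebo: (placebo share from Cohort 1) × q × d, in favour of 3 mg. For 2 mg versus placebo: (2 mg share − placebo share) × q × d, against 2 mg.

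| r | q | d | Placebo ≥ 5 y | 2 mg ≥ 5 y | 3 mg v placebo | 2 mg v placebo |
|---|---|---|---|---|---|---|
| 0.5 | 20% | 5 | 6.7% | 13.3% | 0.33 | 0.33 |
| 1 | 20% | 5 | 10% | 16% | 0.5 | 0.3 |
| 1 | 25% | 10 | 12.5% | 20% | 1.25 | 0.75 |
| 0.5 | 40% | 15 | 13.3% | 26.7% | 2.0 | 2.0 |
| 1 | 40% | 15 | 20% | 32% | 3.0 | 1.8 |

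**5. Scale.** With r = 1, the SE of 3 mg versus placebo is 17.8 × √(1/20.4 + 1/20.4) = 5.57. The worst case is 3.0/5.57 = 0.54 SE, and P(|Z + 0.54| > 1.96) = 8.4% in place of 5%. The middle case of 1.25 points gives 5.5% (t-test, 20 v 20 completers). Against the 20-point target, 1.25 points is 6% and 3.0 points is 15%.

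**6. The planned sensitivity analyses (SAP 10.1).**
- *Analysis 5* adds cohort and SALT I stratum, and keeps the longer episodes.
- *Analysis 6* uses Cohort 2 only, so every eligible subject is under 5 years. It has 24, 6 and 12 planned subjects on 3 mg, 2 mg and placebo.
- *Analysis 7* drops 3 mg, adds cohort and SALT I stratum, and keeps the longer episodes.

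**The case against.** The imbalance comes from unequal cohort mix across arms, not from the mere presence of longer episodes. Within Cohort 1 those episodes are randomized 2:1, so they balance in expectation, and the cohort term in analyses 5 and 7 acts on the difference in mix. Analysis 6 gives 3 mg a concurrent-control comparison at the stated 80% power. Comparisons are exploratory with no formal testing strategy (Protocol 11.7, SAP 5.6), so error-rate inflation carries limited weight. Every input to the bias range is assumed, and the upper end needs all extremes at once, including no Cohort 1 subject lost to the trim although that cohort had a SALT I stratum of 100. The protocol also prespecified disease duration as the covariate without tying it to the current episode.

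Most of this stands, and it rules out three stronger readings that a reader might infer:
- *That the imbalance is unadjusted throughout.* This is true of the primary model only. Analyses 5 and 7 carry a cohort term and analysis 6 removes the longer episodes.
- *That the 3 mg versus 2 mg difference is distorted.* SAP 10.1 limits model-based differences to each active arm against placebo, so no such inferential contrast is planned.
- *That 2 mg has no usable inferential analysis.* Analysis 7 supplies one on all planned 2 mg and placebo subjects who pass the trim. What is thin is inference confined to episodes under 5 years.

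The objection does not reach the primary analysis, which sensitivity runs and descriptive subgroups leave unchanged. Analyses 5 and 7 also do not estimate effects in the population that the protocol describes. They state no cohort-by-visit term, so a gap that widens by Week 24 would be only partly removed; a current-episode covariate entered as a main effect shares that limit.

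**Conclusion.** The point holds for the primary analysis. The population statements in Protocol 3.1 and 3.2 conflict with SAP 3.1, and the primary MMRM leaves an avoidable imbalance in current-episode duration between 3 mg and the other arms, met only by a partial proxy.

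The direction, in favour of 3 mg and against 2 mg relative to placebo, depends on longer episodes responding less. The size is unknown. Under the assumed ranges it is about 0.3 to 3 points for 3 mg versus placebo and 0.3 to 2 points for 2 mg versus placebo, with less if time since onset absorbs part of it. At moderate values it is small against 20 points. The documents do not support saying that the 3 mg effect is exaggerated as a matter of fact.

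For 2 mg, the only inferential analysis confined to episodes under 5 years is analysis 6, with 6 planned subjects and 47% power. The change is worth making because the adjustment is nearly free and improves the headline estimate.

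**What to change.** - **Reconcile** the population statement in Protocol 3.1 and 3.2 with SAP 3.1, so that both give the same episode limit for each cohort.
- **Add current-episode duration** as a covariate in the primary MMRM and the ANCOVA models (SAP 5.2, 10.1 and 10.3). SAP 6.1 already derives it, but the formula there is labelled in years and yields days; divide by 365.25, as 5.2 does.
- **Add one sensitivity run:** the primary MMRM in FAS subjects with a current episode under 5 years.

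The cost is SAP wording, one degree of freedom, some collinearity with time since onset, and one more model run on slightly fewer subjects. No new data are needed.

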3.3. Rationale for Dose Selection

Taken together, the completed and ongoing Phase 1 studies conducted in healthy volunteers with doses up to 4 mg once daily and Phase 2 studies conducted in subjects with ulcerative colitis and atopic dermatitis (AD) patients with dosing up to 2 mg daily demonstrate acceptable tolerability with no significant safety signal.

In the concluded 12-Week Phase 2 Study (Study APD334-201) in subjects with AD, the etrasimod 2 mg dose demonstrated clear efficacy across various measures and demonstrated a greater effect than the etrasimod 1 mg dose. The overall data suggest potential for a higher etrasimod dose to provide a greater clinical benefit to the patient without compromising safety as the overall effect size was moderate for the 2 mg dose and had not plateaued at the Week 12 primary endpoint in the study. Both etrasimod 1 mg and 2 mg doses were well tolerated and there were no unanticipated safety signals.

S1P receptor modulators are associated with an expected, on target dose-dependent effect of reducing HR upon first dosing with HR recovery to predose baseline thereafter (Camm 2014). There have been no reported cases of symptomatic bradycardia on first dose and rare first- or second-degree AV block found on ECG has been asymptomatic and transient (ie, spontaneous resolution) with etrasimod. In Study APD334-003, the mean transient HR decrease did not exceed 10 beats per minute (bpm) on Day 1 up to 8 hours after dosing, with the mean nadir of HR lowering for 2 mg etrasimod occurring 3 hours after dosing. Therefore, a dose escalation regimen is not necessary for doses up to 2 mg. This study includes an etrasimod 3 mg treatment group. To attenuate the magnitude of first dose HR reduction with 3 mg etrasimod, subjects randomized to the 3 mg etrasimod group will receive 2 mg etrasimod daily for the first week and 3 mg etrasimod daily for the remainder of the study (refer to Section 1.2 for additional details).

While ulcerative colitis (UC), Crohn's disease (CD), AD, and AA have similar inflammatory mediated origins, there are differences in pathophysiology, disease location, and extent of disease that may result in a different optimal dose for the treatment of AA. Therefore, this study will evaluate the treatment effect of 2 mg and a higher dose of 3 mg. Based on Phase 1 data in healthy volunteers, Phase 2 data in UC patients, and Phase 2 data in AD patients, etrasimod 2 mg and 3 mg are expected to be safe and well-tolerated in AA patients.

